9.7.2. Extraintestinal Manifestations

During the specified full physical examinations (Table 7), specific systems (such as eyes, liver, skin, and joints) will be examined for EIMs for UC.

9.8. Safety

The Investigator or site staff will be responsible for detecting, documenting, and reporting events that meet the definition of an adverse event or SAE (Section 9.8.8.1). Adverse events will be coded using the latest version of the Medical Dictionary for Regulatory Activities (MedDRA).

9.8.1. Physical Examination

Full and symptom-directed physical examinations will be performed according to the Schedule of Assessments (Table 7).

Full physical examination includes the following assessments:

- General inspection
- Weight
- Skin
- Head/ears/eyes/nose/throat examination
- Neck
- Cardiac examination
- Auscultation of lungs
- Abdominal examination (liver, spleen, and lower abdomen)
- Neurological assessment
- Musculoskeletal assessment to include lower extremity edema evaluation

Symptom-directed (focused) physical examinations should assess clinically significant changes from full physical examinations or any new signs or symptoms.

9.8.2. Vital Signs

Resting vital signs measurements will be performed according to the Schedule of Assessments (Table 7) with the subject in the sitting position. Vital signs will be measured prior to any blood draws that occur at the same study visit.

Blood pressure may be measured manually or by automated device. Proper technique should be utilized during the measurement of BP to include the following:

- The subject's arm should be bare and supported at heart level.
- An appropriately sized cuff (cuff bladder encircling at least 80% of the arm) should be utilized. Subject's legs should not be crossed during the evaluation.

9.8.3. 12-Lead Electrocardiogram

All 12-lead ECGs will be performed according to Section 9.4.1 and the Schedule of Assessments (Table 7), and if clinically indicated at any time during the treatment period per Investigator discretion. All ECGs will be recorded from a 12-lead ECG machine with the subject in the supine position. Every attempt should be made to ensure the subject 12-lead ECG readings are obtained using the same machine throughout the study.

Intervals to be provided on the confirmed read for each safety 12-lead ECG are: RR, PR, QRS, QT, and Fridericia's corrected QT interval (QTcF). If an ECG shows a new onset QTc interval > 500 ms during the treatment period, a repeated ECG is warranted. If this abnormal finding is confirmed, study treatment must be interrupted. Effective diagnostic and therapeutic strategies should be employed.

Reversible causes of prolonged QTc interval (eg, electrolyte abnormalities or hypomagnesemia), should be corrected as clinically indicated. When evaluating a subject with new onset QTc interval above 500 ms, referral to a cardiologist experienced in treating cardiac conduction disorders should be considered. Re-initiation of study treatment can only be considered after all of the following have occurred:

- The QTcF interval is < 450 ms (men) or < 470 ms (women).
- The QTc prolongation is considered by the Investigator and confirmed by the cardiologist as not related to study treatment and likely caused by other factors.
- Individual risk-benefit is favorable (as determined by the Investigator, in agreement with the cardiologist), **AND**
- After discussion with the Medical Monitor.

The Investigator will be responsible for review and interpretation of 12-lead ECGs on site and determining if the 12-lead ECG is normal, abnormal clinically insignificant, or abnormal clinically significant. Findings will be documented in the eCRF.

All 12-lead ECGs performed should be available for collection upon request.

9.8.4. Pulmonary Function Test

[figure not shown]
Pulmonary function tests will be performed according to the Schedule of Assessments (Table 7) and includes FEV₁ and FVC measurements. All subjects will have PFTs performed at Week 52 or at the Early Termination visit.

Subjects with a history of mild pulmonary disease (eg, asthma, chronic obstructive pulmonary disease) will have additional PFTs performed at Week 32. Subjects reporting respiratory adverse events such as dyspnea during the treatment period may return at an unscheduled visit for assessment per Investigator discretion; additional PFTs may be performed as clinically indicated.

Subjects experiencing a decline in PFT values (FEV₁ and/or FVC) below 50% of the predicted values must be discontinued from study treatment and scheduled for a follow-up visit.

At sites where available, diffusing capacity of the lungs for carbon monoxide (DLCO) measurements will also be performed (sites where DLCO is not available should consult the Sponsor or Sponsor's delegate). These tests will be performed at a qualified pulmonary function

laboratory or respiratory department. Please refer to the American Thoracic Society/European Respiratory Society guidelines for standardization of spirometry and single breath determination of carbon monoxide uptake in the lung (MacIntyre 2005, Miller 2005a, Miller 2005b).

9.8.6. Tuberculosis Ouestionnaire

For subjects who are receiving TB prophylaxis treatment, the TB questionnaire will be completed at every study visit (until TB prophylaxis treatment course is completed).

9.8.7. Clinical Laboratory Tests

Refer to Table 6 for the list of clinical laboratory tests to be performed and the Schedule of Assessments (Table 7) for timing and frequency for each test. Details regarding clinical laboratory sample collection, preparation, and shipment are provided in the Laboratory Manual by the central laboratory.

Clinical safety laboratory tests should be completed predose. The Investigator must review the laboratory report, document this review, and record any clinically relevant changes occurring during the study in the adverse event section of the eCRF (results of the total WBC and ALC will be reviewed and monitored as described in Section 9.7.4). The laboratory reports must be filed with the source documents. Clinically significant abnormal laboratory findings are those that are not associated with the underlying disease, unless judged by the Investigator to be more severe than expected for the subject's condition.

All laboratory tests with values considered clinically significantly abnormal during participation in the study or within 30 days after the last dose of study treatment should be repeated until the

values return to normal or baseline or are no longer considered clinically significant by the Investigator or Medical Monitor.

- If such values do not return to normal/baseline within a period of time judged reasonable by the Investigator, the etiology should be identified, and the Sponsor should be notified.
- All protocol-required laboratory assessments, as defined in the Schedule of Assessments (Table 7) must be conducted in accordance with the Laboratory Manual.
- If laboratory values from non-protocol-specified laboratory assessments performed at the institution's local laboratory require a change in subject management or are considered clinically significant by the Investigator (eg, adverse event, SAE, or dose modification), then the results must be recorded in the eCRF.

For guidance on monitoring subjects with notable lymphopenia, please refer to Section 9.7.4.

Table 6: Clinical Laboratory Tests

PREGNANCY TESTING Urine β-hCG (only for women of c	hildbearing potential)			
CLINICAL CHEMISTRY, HEMATOLOGY, AND COAGULATION				
Hematology	Serum Chemistry			
CD4 T-cell count ^a	Alanine aminotransferase	Potassium		
Hematocrit	Albumin	Sodium		
Hemoglobin	Alkaline phosphatase	Thyroid-stimulating hormone		
Mean corpuscular hemoglobin	Aspartate aminotransferase	Thyroxine free		
Mean corpuscular hemoglobin	Bicarbonate	Total bilirubin		
concentration	Blood urea nitrogen	Total cholesterol		
Mean corpuscular volume	C-reactive protein	Total protein		
Platelet count	Calcium	Triglycerides		
Red blood cell count	Chloride	Triiodothyronine free		
White blood cell count with	Creatinine	Uric acid		
differential ^a	Creatine kinase			
Coagulation	Direct bilirubin			
Activated partial thromboplastin	Gamma-glutamyl transferase			
time	Glucose			
International normalized ratio	Lactate dehydrogenase			
Prothrombin time	Phosphorus			
TUBERCULOSIS TESTING				
QuantiFERON				
URINALYSIS				
Appearance	Microscopic examination of	Specific gravity		
Bilirubin	sediment	Urobilinogen		
Color	Nitrite			
Glucose	Occult blood			
Ketones	pН			
	Protein			

Table 6: Clinical Laboratory Tests (Continued)

^a Total WBC, neutrophil, lymphocyte, and CD4 T-cell counts will be reviewed by an unblinded Medical Monitor who will provide instructions to the site investigator in the event of significant lymphopenia. Investigators will remain blinded to the results. Refer to Section 9.7.4 for additional details.

9.8.7.1. Pregnancy Testing

Urine pregnancy tests (β -hCG) should be performed as indicated in the Schedule of Assessments (Table 7). A monthly home pregnancy test in non-visit months should be performed and any positive result immediately reported to the study site. If a home pregnancy test is unavailable, the pregnancy test will be performed on site during an unscheduled visit. If at any point there is a case of a positive urine β -hCG test, the subject will have study treatment interrupted and a serum sample submitted to the central laboratory for β -hCG testing. If the serum test confirms positive, the subject will be withdrawn from the study treatment and all the necessary follow-up assessments will be conducted as per Section 9.8.9. If the serum test is negative, the subject may resume study treatment.

Negative pregnancy test results must be documented for all women of childbearing potential prior to dosing at applicable study visits. Women who are surgically sterile or who are postmenopausal are not considered to be of childbearing potential. Postmenopausal is defined as 12 consecutive months with no menses without an alternative medical cause.

9.8.7.2. Clinical Chemistry, Hematology, Coagulation, and Urinalysis

Clinical chemistry, hematology, coagulation, and urinalysis parameters that will be assessed during the study are identified in Table 6.

Subjects will be in a seated or supine position during blood collection. All laboratory samples should be collected prior to the administration of study treatment at applicable visits (refer to Section 9.6 for timing of blood draws for PK).

9.8.8. **Adverse Events**

9.8.8.1. **Definitions**

9.8.8.1.1. Adverse Event

An adverse event is any untoward medical occurrence in a subject or clinical investigational subject administered a medicinal product and which does not necessarily have a causal relationship with this treatment. An adverse event can therefore be any unfavorable and unintended sign, symptom, or disease temporally associated with the use of a medicinal product, whether or not considered related to the medicinal product.

Adverse events can be any of the following:

- Unfavorable changes in general condition
- Subjective or objective signs/symptoms
- Concomitant disease or accidents
- Clinically relevant adverse changes in laboratory parameters over the course of the study
- Preexisting conditions that worsen in severity, increase in frequency, or have new signs/symptoms

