5. REMOVAL OF SUBJECTS FROM STUDY TREATMENT OR ASSESSMENT

5.1. Discontinuation from Study Treatment

A subject's double-blind treatment may be discontinued for any of the following reasons:

- Worsening of disease (Note: If a subject discontinues double-blind treatment at any time, the subject may be eligible to enter the APD334-303 OLE study [Section 5.1.1])
- Adverse event that in the judgement of the Investigator and/or Medical Monitor the subject should not continue study treatment
- Subject noncompliance with the protocol or study treatment that is considered significant by the Medical Monitor
- Investigator decision
- Withdrawal by subject or parent/guardian
- Lack of efficacy
- Lost to follow-up
- Study termination by Sponsor
- Other, non-adverse event

A subject's double-blind treatment must be discontinued for any of the following reasons:

- Decline in PFT values (forced expiratory volume at 1 second [FEV₁] and/or forced vital capacity [FVC]) below 50% of the predicted values
- Confirmed diagnosis of clinically significant macular edema
- Confirmed diagnosis of active tuberculosis (TB)
- Subjects who have a cardiovascular treatment-related symptomatic event (eg, chest pain, dizziness, palpitations, lightheadedness, shortness of breath, or syncope) associated with reduction of the heart rate or associated with clinically relevant ECG changes at any time during the 4-hour monitoring period on the first or second day after re-initiation of treatment after a dose interruption of ≥ 7 days (Section 9.4.1)
- Subjects who have not met the discharge criteria on the first day of re-initiation of treatment after ≥ 4 hours of extended monitoring, or on the second day of re-initiation by 4 hours postdose.
- Pregnancy (Section 9.8.9)
- Suspected drug-induced liver injury as defined by the 2009 FDA Guidance for Industry (FDA 2009):
 - Alanine aminotransferase (ALT) or aspartate aminotransferase (AST) > 8 × upper limit of normal (ULN)
 - ALT or AST $> 5 \times ULN$ for > 2 weeks

- ALT or AST $> 3 \times$ ULN and (total bilirubin $> 2 \times$ ULN or international normalized ratio > 1.5)
- ALT or AST $> 3 \times$ ULN with the appearance of fatigue, nausea, vomiting, right upper quadrant pain or tenderness, fever, rash, and/or eosinophilia (> 5%)

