9.8.8.1.2. Serious Adverse Event

An adverse event should be classified as an SAE if it meets one of the following criteria:

Fatal: Adverse event resulted in death.

Life-threatening: The adverse event placed the subject at immediate risk of death. This

classification does not apply to an adverse event that hypothetically

might cause death if it were more severe.

Hospitalization: The adverse event required or prolonged an existing inpatient

hospitalization. Hospitalizations for elective medical or surgical

procedures or treatments planned before the signing of informed consent

in the study or routine check-ups are not SAEs by this definition.

Disabling/ The adverse event resulted in a persistent or significant incapacity or incapacitating:

substantial disruption of the subject's ability to conduct normal life

functions.

Congenital anomaly

or birth defect:

An adverse outcome in a child or fetus of a subject exposed to the molecule or study treatment regimen before conception or during

pregnancy.

Medically The adverse event did not meet any of the above criteria but could have significant:

jeopardized the subject and might have required medical or surgical intervention to prevent one of the outcomes listed above or involves suspected transmission via a medicinal product of an infectious agent.

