9.8.8.3.1. Serious Adverse Events

Any adverse event considered serious by the Investigator or that meets serious criteria must be reported to the designated safety contact within 24 hours of becoming aware of the event. Enter the SAE information into eCRF, and send other available pertinent information (eg, hospital records, laboratory results) to the designated Sponsor Contact (IQVIA). If additional information is required or becomes available for a previously reported SAE, entry of the new information into eCRF should be completed within 24 hours of awareness.

In case of electronic data capture (EDC) connectivity issues (eg, the eCRF cannot be accessed by the Investigator), the Investigator must complete a Back-Up Paper SAE Report Form and send the form to the designated Sponsor Contact (IQVIA) within **24 hours of investigator awareness of the event.** Once the EDC connectivity is restored, the investigator must enter all pertinent information from the Back-Up Paper SAE Report Form into the eCRF as soon as possible.

For the reporting of Pregnancy/Pregnancy Outcome SAEs, and SAEs occurring after the protocol-defined collection period, the investigator must complete a Back-Up Paper SAE Report Form and send the form to the Sponsor Contact (IQVIA) within 24 hours of investigator awareness of the event.

IQVIA Pharmacovigilance

[contact] (access code [name])

[contact]

Email (preferred method): [contact]

Elective hospitalization and/or surgery for clearly preexisting conditions (eg, a surgery that has been scheduled prior to the subject's entry into the study) will not be reported as an SAE. All other hospitalizations, including elective hospitalizations for any condition that was not preexisting, will be reported as an SAE.

Any SAE that is ongoing when the subject completes the study or discontinues the study will be followed by the Investigator until the event resolved, stabilized, or returned to baseline status.

The Sponsor (via the In-Country Caretaker for Clinical Trial [ICCC]) is responsible for notifying the relevant regulatory authorities of any adverse event assessed by the Reporter (PI) or the Sponsor as:

- a) Serious, unexpected, and related, or
- b) Serious, expected, related and life-threatening or fatal

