16.1.2. Missing Data Methods for Primary Efficacy Variable

Subjects who 1) discontinue the study for lack of efficacy, or adverse event related to UC, 2) initiate a rescue medication for UC, 3) have an increase in dose over Baseline levels in their existing UC medication, or 4) have rescue medical procedure (e.g., colectomy, ileostomy, or sigmoidectomy) during the study as confirmed after blinded review by clinical and medical team members before study unblinding will be considered to have a known (i.e., non-missing) outcome of nonresponse in the analysis of all efficacy endpoints at any subsequent timepoints, including the primary endpoint. The rescue medications will be identified by the Arena clinical team during blinded data review. Refer to APPENDIX 6APPENDIX 6 for the definition of rescue therapies (medication and medical procedures). In scenarios #2 and #3 above, if a subject has efficacy measurement collected after the initiation or dose increase from Baseline of UC medication, the observed data will be censored at the time of initiation or dose increase and they will be considered having a nonresponse. Subjects in all 4 scenarios above may still be included in the respective Per Protocol Set, provided they do not violate other criteria for Per Protocol Set. For example, they will be excluded from the respective Per Protocol Set if they initiate a prohibited medication before Week 52 efficacy assessment that can affect efficacy of the study

treatment and the indication is unrelated to UC.

Analysis visits will be mapped as per Section 6.4 before any missing data imputation method is applied.

Subjects with missing efficacy outcome will be included in the primary analyses using single imputation as nonresponder. Supplementary analyses of efficacy outcomes will be performed in modified Full Analysis Set with data as observed.

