17.1.6. UC-RELATED HOSPITALIZATIONS AND SURGERIES

The UC-related hospitalizations will be captured on the Adverse Event eCRF. The UC-related surgeries, including colectomy, are captured on the Non-Drug Treatment eCRF. Blinded review of AE preferred terms will be performed to determine UC-related hospitalizations.

The UC-related surgeries, including colectomy, will be captured on the Concomitant Non-Drug Treatment eCRF.

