18.1.6. Overall Summary of Adverse Events

In addition to the summaries above, an overview of TEAEs will be summarized (not broken down by SOC or PT) by number and percentage of subjects and by number of AEs:

- Any TEAEs
- Any related TEAEs
- Any serious TEAEs
- Any related serious TEAEs
- TEAEs leading to death

- Liver-related TEAEs leading to death
- TEAEs leading to study drug discontinuation
 - Related TEAEs leading to study drug discontinuation
 - Liver-related TEAEs leading to study drug discontinuation
- TEAEs leading to study drug interruption
 - Related TEAEs leading to study drug interruption
- TEAEs by maximum severity
 - Related TEAEs by maximum severity
- TEAEs by relationship to study drug

*Related TEAEs' refers to TEAEs related or probably related to study drug.

Comparative analyses will be performed for:

- Deaths
- Serious TEAEs
- TEAEs leading to study treatment discontinuation
- TEAEs of special interest
- Serious infections
- Opportunistic infections (Narrow)
- Malignancies

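### SAP 18.1.6 compares serious TEAEs and TEAE discontinuations between arms with no UC-excluded version, so a higher placebo UC event rate could offset a non-UC excess on etrasimod in those totals

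*Protocol*

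**What the plan says.** - **Adverse event definition.** Protocol 9.8.8.1.1 says that adverse events can include "Preexisting conditions that worsen in severity, increase in frequency, or have new signs/symptoms". It makes no exception for the disease under study.
- **UC events as adverse events.** SAP 16.1.2 assigns nonresponse to subjects who "discontinue the study for lack of efficacy, or adverse event related to UC". SAP 17.1.6 states: "The UC-related hospitalizations will be captured on the Adverse Event eCRF".
- **Seriousness.** Protocol 9.8.8.1.2 makes an event serious where "The adverse event required or prolonged an existing inpatient" stay. Protocol 9.8.8.3.1 exempts only "Elective hospitalization and/or surgery for clearly preexisting conditions". An unplanned UC admission is therefore serious.
- **Discontinuation.** Protocol 5.1 lists disease worsening ("Worsening of disease (Note: If a subject discontinues double-blind treatment at any time"), lack of efficacy and adverse event as separate reasons. SAP 18.1.2 identifies TEAE discontinuations from the action recorded on the adverse event page.
- **Arm comparisons.** SAP 18 rules out safety comparisons unless specified otherwise. SAP 18.1.6 specifies them for several categories, including serious TEAEs and "TEAEs leading to study treatment discontinuation". It names no method and no UC-excluded version.

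**The concern.** In a placebo-controlled UC trial, disease worsening is the outcome the drug is meant to reduce. If it does so, placebo collects more UC events. Those recorded as adverse events raise the placebo totals for a reason that belongs to efficacy. A similar or lower total on etrasimod would then not show that events other than UC worsening are balanced, and that balance matters most for the long-term safety objective in Protocol 2.3.

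The serious TEAE comparison is the more exposed of the two, because unplanned UC admissions enter it by definition. The discontinuation comparison is exposed only when the site records the flare on the adverse event page with drug withdrawal as the action taken.

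**Working it through.** The documents state no rate, power or sample size for these comparisons, so there is no figure of the plan's own to reproduce. The check asks how large a UC imbalance would have to be to matter.

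**Inputs from the documents.** About 35 Japanese subjects (Protocol 10.2) and 2:1 allocation (Protocol 6.1): 35 × 2/3 ≈ 23 on etrasimod, leaving 12 on placebo. SAP 6.5 notes that the ratio was not controlled within Japan, so this split is approximate.

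**Assumed inputs.** The serious-event rates for UC and non-UC events in each arm. The two kinds of event are taken as independent within a subject.

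**Formula.** Total rate = 1 − (1 − non-UC rate)(1 − UC rate).

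**Exact offset.** Take non-UC 15% v 5% (etrasimod v placebo) and UC 5% v 15%.
- Etrasimod: 1 − 0.85 × 0.95 = 19.25%.
- Placebo: 1 − 0.95 × 0.85 = 19.25%.

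The assumed 10-point excess is gone. This does not depend on independence: if no subject has both kinds of event the rates add, giving 15 + 5 = 20% and 5 + 15 = 20%.

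**Smaller excess.** Take non-UC 10% v 2% and vary the UC rates. The last column is the exact binomial probability, at 23 v 12, that the observed difference is zero or favors etrasimod.

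| UC rate, etrasimod v placebo | Total, etrasimod | Total, placebo | Difference (points) | Chance of seeing no excess |
|---|---|---|---|---|
| UC terms excluded | 10.0% | 2.0% | +8.0 | 0.15 |
| 3% v 3% | 12.7% | 4.9% | +7.8 | 0.17 |
| 3% v 10% | 12.7% | 11.8% | +0.9 | 0.41 |
| 3% v 15% | 12.7% | 16.7% | −4.0 | 0.56 |
| 5% v 20% | 14.5% | 21.6% | −7.1 | 0.65 |

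**Break-even.** Setting the two totals equal gives: placebo UC rate = 1 − (1 − non-UC etrasimod)(1 − UC etrasimod)/(1 − non-UC placebo). With an etrasimod UC rate of 0 to 5%, the placebo UC rate that cancels the excess is:
- 8 to 13% for non-UC 10% v 2%;
- 11 to 15% for 15% v 5%;
- 16 to 20% for 20% v 5%.

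So a UC gap of roughly the same number of points as the non-UC excess hides it. When UC rates are equal, almost nothing is lost.

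**Significance.** With UC terms removed, the power of a two-sided Fisher test at 0.05 to show the excess is 0.1%, 0.8% and 4.0% in the three scenarios. With 0/12 on placebo, at least 8/23 on etrasimod are needed (p = 0.032). The distortion is therefore in the point estimates and how they are read.

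**The case against.** The strongest reply is that the plan already shows disease activity in several places. SAP 17 compares UC-related hospitalizations between arms by the method of 16.1.3, using the blinded preferred-term review in 17.1.6. All TEAEs, serious TEAEs and TEAE discontinuations are tabulated by system organ class and preferred term. Serious TEAEs and TEAE discontinuations are also listed. SAP 18.1.6 compares special-interest events, serious infections, opportunistic infections and malignancies separately, so an excess there would appear whatever the UC event rate. With so few subjects, a reader could sort the serious cases by hand.

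All of this stands, and it limits the point to the compared totals. It does not remove it. Preferred-term counts cannot simply be subtracted to give subjects with any non-UC event, because one subject may have both kinds. A term list chosen from the listings after unblinding is not prespecified.

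A term list also has its own risk. Diarrhea is a UC symptom (Protocol 1.1) and a reported effect of this drug class (Protocol 1.3), so a broad list could remove real drug harm. That is a reason to keep the list narrow.

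Some stronger readings are tempting but not supported:
- **Every flare is an adverse event.** Protocol 9.8.8.1.1 says what adverse events can be, and Protocol 5.1.1 also covers UC that has merely not improved.
- **Nothing in the plan separates disease activity.** The outputs listed above do.
- **The exposure-adjusted rates are affected in the same way.** SAP 18.1.1 plans them by system organ class and preferred term only.
- **Protocol 9.8.7 takes the opposite line for laboratory findings.** It says "Clinically significant abnormal laboratory findings are those that are not associated with the underlying disease", but it still admits findings judged more severe than expected.
- **Using one event for both efficacy and safety is an error.** One event may properly inform both.

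**Conclusion.** The point holds in a limited form. UC worsening may enter the totals of any TEAE and of serious TEAEs, and it enters TEAE discontinuations when drug withdrawal is recorded on the adverse event page. The two comparisons in SAP 18.1.6 have no UC-excluded counterpart, so a non-UC excess on etrasimod can be offset there if placebo has more UC events.

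The size is illustrative, because every event rate used is an assumption. A reader might infer that the plan will hide harm, or that it has been hidden already in the programme. The documents do not show either. The phase 2 figures in Protocol 3.2 are mixed. Serious adverse events were 0% on 2 mg and 11.1% on placebo, which fits the direction, but the UC share is not given. TEAE discontinuations were 8.0% and 0%, which shows no masking.

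At about 23 v 12 the comparisons could hardly establish harm with or without UC terms. What is at stake is whether a balanced total is read as reassurance.

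**What to change.** In SAP 18.1.6, keep all planned totals unchanged. Beside them, add matching overview rows and arm comparisons that exclude UC-worsening preferred terms, primarily for serious TEAEs and also for TEAEs leading to discontinuation of study treatment. This follows a pattern the section already uses, since it carries liver-related sub-rows defined by system organ class and preferred term in 18.1.2.

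Fix the term list before unblinding by extending the blinded preferred-term review in SAP 17.1.6, which at present covers hospitalizations only. Keep it to terms that denote worsening of UC itself. Leave off non-specific symptoms that may be drug effects, such as diarrhea. Read the two versions together when drawing the safety conclusion. The exposure-adjusted rates need no change.

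The cost is a small extra blinded review and a few more rows, with no new data. Some misclassification will remain, because any term list leaves borderline events on one side or the other.
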